6.4 Special Statistical/Analytical Issues

6.4.1 Discontinuations and Missing Data

Primary and secondary effectiveness endpoints

For analysis of the primary and secondary effectiveness endpoints the following conventions will be applied: if data from the independent evaluators is completely missing (e.g., for all 3 evaluators), the multiple imputation method will be employed as described above for the primary and secondary analysis. For the worst case analysis, the subject will be analyzed as having “no improvement”.

[figure not shown]
The following procedure for incomplete data from the independent evaluators will be applied:

- If the result of two out of three evaluators is missing, the outcome of the subject will be set to missing and the multiple imputation technique will be applied for the primary analysis. The subject will not be included in the observed case analysis and for the worst case analysis, the subject will be analyzed as having “no improvement”.
- If the result of one evaluator is missing and the other two evaluators agree on the assessment “improvement” then the outcome of the subject is set to “improvement” for all analyses.
- If the result of one evaluator is missing and the other two evaluators agree on the assessment “no improvement” then the outcome of the subject is set to “no improvement” for all analyses.
- If the result of one evaluator is missing and the other two evaluators disagree, then the outcome of the subject will be set to missing and the multiple imputation technique will be applied for the primary analysis. The subject will not be included in the observed case analysis and for the worst case analysis, the subject will be analyzed as having “no improvement”.

All other effectiveness data will be analyzed as observed with no imputation of missing values. The denominator for percentages will be all subjects in the respective analysis set or population

(i.e., missing data for binary or categorical variables will be presented as a separate possible category ‘Missing’).

CCI

Adverse events

For any missing data of adverse events, a worst case strategy will be applied for all analysis tables. The intensity will be imputed by the worst intensity “severe”, the causal relationship will be imputed by the worst relationship “related”. Missing data of the outcome will be imputed by “unknown”.

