6.1.1 Primary Effectiveness Endpoints

6.1.1.1 Primary analysis

The primary endpoint of the study is the proportion of treated subjects with improvement in lines and wrinkles of the décolleté by comparing photographs taken at Day 90 (post-treatment) with baseline (pre-treatment) photographs.

Each independent evaluator will assess “Improvement” or “No Improvement” between Photograph 1 (baseline) and Photograph 2 (post-baseline). Photograph 1 will be identified, and the independent evaluators will be blinded to the random distribution of treated versus untreated status of the comparator Photograph 2 (i.e., Day 90 post-treatment among treated subjects or post-baseline for untreated individuals). If photographs are declared as not assessable during the Day 90 assessment session, the evaluators will be instructed to rate the corresponding Photograph 2 as “No Improvement”.

Improvement will be declared if at least two blinded evaluators indicate “Improvement” for the comparator photograph. In case at least two evaluators declare a photograph as not assessable, the corresponding improvement score over all evaluators will be set to missing for the primary analysis.

The point estimate for the proportion of subjects fulfilling the primary endpoint will be described by frequency statistics for the ITT subset.

Effectiveness is established if:

- A. the point estimate is $\geq 65\%$ and
- B. the lower bound of the one-sided 95% Wilson CI is $> 50\%$.

Missing data, including a missing primary endpoint assessment in subjects with unacceptable or missing photographs at baseline or Day 90, will be imputed by multiple imputation. In case of complete data, no multiple imputation will be performed and the primary analysis is based on complete data for the ITT.

Imputation is done 50 times using a fully conditional specification logistic regression method, as implemented in SAS PROC MI with statement FCS LOGISTIC, and will use the investigational site and the baseline characteristics age and BMI as independent variables.

In a first step a total of $m=50$ imputed datasets will be generated, where missing data in the primary endpoint (improvement over all evaluators) is modelled via logistic regression based on input variables site, age and BMI at baseline. CCI

CCI

CCI

CCI response is coded as (0=no response (“no improvement”), 1=response (“improvement”)). The two-sided 90% Wilson CI ([WL, WU]) will be calculated using the following steps, as detailed in [1]:

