6.1.2 Secondary Effectiveness Endpoint

The secondary endpoint will only be assessed among subjects reconsented for extended study participation.

The secondary endpoint of the study is the proportion of treated subjects with improvement in lines and wrinkles of the décolleté by comparing photographs taken at Day 180 (post-treatment) with baseline (pre-treatment) photographs.

Each independent evaluator will assess “Improvement”, “No Improvement” or “Cannot Evaluate” between Photograph 1 (baseline) and Photograph 2 (post-baseline). Photograph 1 will be identified, and the independent evaluators will be blinded to the random distribution of treated versus untreated status of the comparator Photograph 2 (i.e., Day 180 post-treatment among treated subjects or post-baseline for untreated individuals). If photographs are declared as not assessable during the Day 180 assessment session, the evaluators will be instructed to rate the corresponding Photograph 2 as “Cannot Evaluate”.

Improvement will be declared if at least two blinded evaluators indicate “Improvement” for the comparator photograph. In case at least two evaluators declare a photograph as not assessable (i.e., “Cannot Evaluate” is ticked), the corresponding improvement score over all evaluators will be set to missing for the secondary analysis. In case one evaluator rates a photograph as “Cannot Evaluate” and the other two evaluators disagree, the overall improvement score will be set to “No Improvement”.

[figure not shown]
The proportion of subjects fulfilling the secondary endpoint will be described by frequency statistics for the ITT subset, including the one-sided 95% Wilson CI.

Missing data, including a missing secondary endpoint assessment in subjects with unacceptable, not assessable or missing photographs at baseline or Day 180, will be imputed by multiple imputation. In case of complete data, no multiple imputation will be performed and the primary analysis is based on complete data for the ITT.

Imputation is done 50 times using a fully conditional specification logistic regression method, as implemented in SAS PROC MI with statement FCS LOGISTIC, and will use the investigational site and the baseline characteristics age and BMI as informing variables. Point estimate and Wilson CI will be calculated with methods as described in Section 6.1.1.1. For implementation, SAS code similar to the statements for the primary endpoint will be used.

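### With one unusable read and the other two split, the SAP gives conflicting outcomes, and its imputation model ignores the two reads in hand

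*SAP*

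**What the plan says.** SAP 6.4.1 opens with "For analysis of the primary and secondary effectiveness endpoints the following conventions will be applied". With one result missing, a pair keeps its outcome if the other two reads agree. If one result "is missing and the other two evaluators disagree, then the outcome of the subject will be set to missing", the pair goes to multiple imputation, leaves the observed-case analysis, and counts as no improvement in the worst-case analysis. For two absent reads: "If the result of two out of three evaluators is missing, the outcome of the subject will be set to missing".

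SAP 6.1.2 (Day 180) allows three answers: Improvement, No Improvement and Cannot Evaluate. If one evaluator answers Cannot Evaluate and "the other two evaluators disagree, the overall improvement score will be set to “No Improvement", the pair is a definite non-responder. If two evaluators answer Cannot Evaluate, the score is set to missing. The same section lists not-assessable photographs among the missing data to be imputed.

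SAP 6.1.1.1 (Day 90) handles a not-assessable photograph differently: "the evaluators will be instructed to rate the corresponding Photograph 2 as “No Improvement". It also sets the overall score to missing if at least two evaluators declare the photograph not assessable.

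What is imputed is the overall score. It "is modelled via logistic regression based on input variables site, age and BMI at baseline", and SAP 6.1.2 names the same three variables. The individual reads do not appear in the visible text; some adjoining text is redacted.

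**The concern.** At Day 180 a pair with one Improvement, one No Improvement and no usable third read is a failure under 6.1.2. Under 6.4.1 it is an imputed value near the average rate. Which rule applies depends on whether Cannot Evaluate counts as a missing result, and the SAP does not say.

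Two further problems sit behind this. First, 6.1.2 is not monotone on its own terms: {Cannot Evaluate, Improvement, No Improvement} scores 0, while {Cannot Evaluate, Cannot Evaluate, No Improvement} is imputed near the average. The pair with more positive evidence gets the lower score. Second, 6.4.1 removes only the split pairs, so missingness depends on the observed reads. An imputation model without those reads cannot correct for that.

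At Day 90 an evaluator who finds the photograph not assessable is recorded as No Improvement, so a split among the other two is a failure. If the same read is simply absent, 6.4.1 imputes the pair.

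At stake is a Day 180 rate that moves with an unsettled choice of wording, and a smaller ambiguity in the primary endpoint.

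**Working it through.** **The plan's own figure.** SAP section 3 assumes a 70% responder rate and states 80 evaluable subjects for at least 85% power. By exact binomial calculation at n = 80, the smallest count meeting both success conditions is 52 (65.0%, Wilson lower limit 55.9%), with power 0.863. The figure reproduces, and the 65% condition binds. At N = 90, 58/90 = 64.4% fails and 59/90 = 65.6% passes.

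**Assumptions.** The majority rate is 70%, from the SAP. Readers are exchangeable and reads are lost at random. Site, age and BMI carry no information, so imputation gives about 0.70. The documents give neither a rate of unusable reads nor a level of reader agreement, so both are varied.

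**Formulas.** Let s be the probability that two reads split, c the probability that the third read is Improvement given a split, and f the fraction of pairs with exactly one unusable read. Relative to a full three-read result:

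- No Improvement rule: shift = -f × s × c
- Imputation rule: shift = f × s × (0.70 - c)

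**Case 1: 5% of reads unusable, independently.** f = 3 × 0.05 × 0.95² = 0.135. The reader model is probit-normal with latent correlation 0.2 to 0.8 (kappa 0.12 to 0.58), calibrated to a 70% majority rate. With E1, E2 and E3 the first three moments of the subject-level read probability, solve 3E2 - 2E3 = 0.70; then s = 2(E1 - E2) and c = 2(E2 - E3)/s.

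| Latent correlation | s | c | No Improvement rule | Imputation rule |
|---|---|---|---|---|
| 0.2 | 0.398 | 0.62 | -3.3 points | +0.43 points |
| 0.8 | 0.180 | 0.56 | -1.4 points | +0.35 points |

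Intermediate correlations give up to +0.44 for the imputation rule. The gap between the rules is 1.7 to 3.8 points. With 10% of reads unusable the shifts are -2.5 to -6.0 and +0.6 to +0.8.

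**Case 2: 5% of subjects with one unusable read.** f = 0.05. The reader model is beta-binomial with inter-read correlation 0 to 0.5.

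- Correlation 0 (s = 0.463, c = 0.637): -0.05 × 0.463 × 0.637 = -1.5 points; +0.05 × 0.463 × 0.063 = +0.15.
- Correlation 0.5 (s = 0.215, c = 0.562): -0.05 × 0.215 × 0.562 = -0.6 points; +0.05 × 0.215 × 0.138 = +0.15.

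Of 90 subjects, about 1 to 2 would be affected split pairs. With 2% of subjects the shifts are -0.2 to -0.6 and about +0.06.

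**Sign of the imputation rule.** Its shift per affected pair is the true rate minus c. In the exchangeable model this is zero at a true rate of 50% and -0.03 to -0.08 at 40%. At 70% it also reverses if the absent reader is lenient: an own rate of 0.8 or 0.9 gives -0.1 or -0.2. The same happens if non-responders are always read No Improvement and responders are read Improvement with probability 0.8 to 0.9. Every split then comes from a responder, c is 0.8 to 0.9, and the shift is -0.1 to -0.2.

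**Two unusable reads.** In the probit model the chance of majority improvement is 0.16 to 0.36 if the one usable read is No Improvement, and 0.88 to 0.94 if it is Improvement. The plan imputes about 0.70 for both.

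**Primary success probability (N = 90, reads nearly independent).** With all reads it is 0.85. Under the 6.4.1 rule it is 0.85, 0.85 and 0.86 with 5, 10 and 20% of subjects affected. If single unusable reads instead count as No Improvement, it is 0.77, 0.65 and 0.43. Those last values need Day 90 reads to be unusable at the assumed rates.

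**The case against.** The strongest reply is that 6.1.2 follows the endpoint as written. Improvement needs at least two positive reads, and {Cannot Evaluate, Improvement, No Improvement} has one. It understates only against a hypothetical third read. Cannot Evaluate is also a recorded answer, so separate rules for a recorded answer and an absent read could have been intended. The literal-definition point stands, and the separate-rules reading is possible. But no sentence states it, 6.1.2 itself lists not-assessable photographs as missing data, and the non-monotone scoring lies wholly inside 6.1.2.

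A second reply is that the material effect is on an endpoint with no success criterion, and that the worst-case analysis scores a split pair as no improvement under either rule. Both statements are correct and limit the weight of the point.

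A third reply concerns size. Five percent of reads is about 13.5% of pairs with exactly one unusable read, and independence is doubtful because all three evaluators see the same images. This stands, and is why the per-subject figures are given as well.

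Three stronger readings are tempting and unsupported. A reader might infer that the two rules always bias in opposite directions; the sign of the 6.4.1 rule depends on the true rate and on the readers. A reader might infer that the primary rate is pushed up towards 65%. But 6.1.1.1 rates unassessable Day 90 photographs No Improvement, so 6.4.1 acts only on absent reads, which should be few in a proctored, two-choice session. A reader might take the contrast of 0.16-0.36 with 0.88-0.94 as bias. With reads lost at random these average to 70%, so it shows lost information.

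**Conclusion.** The concern holds in a limited form. The SAP gives conflicting outcomes for one unusable read with a split, leaves the status of a single Cannot Evaluate undefined, scores non-monotonically within 6.1.2, and visibly imputes without the available reads.

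At a 70% rate with exchangeable readers, the Day 180 shift from a three-read result is -1.4 to -3.3 points under 6.1.2 and about +0.4 under 6.4.1 if 5% of reads are unusable independently. It is -0.6 to -1.5 and +0.15 if 5% of subjects are affected. The downward direction under 6.1.2 is certain; the upward direction under 6.4.1 is conditional.

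At Day 90 the effect should be under 1 point, provided single unusable reads are rare; at 2% of subjects even the No Improvement rating costs at most 0.6 points. The documents do not show that the primary conclusion is at risk. With one subject able to decide the 65% condition, the rule should still be settled before the reads are seen. This should be corrected, but it does not undermine the trial.

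**What to change.** 1. State that Cannot Evaluate and absent reads are both missing reads. Apply one rule per endpoint, worded alike in SAP 6.1.1.1, 6.1.2 and 6.4.1. For Day 90, say whether a not-assessable declaration by one evaluator keeps its No Improvement rating or is a missing read; treating it as missing would match Day 180.
2. For the main multiple-imputation analysis, impute the missing individual reads by FCS LOGISTIC, with the other reads plus site, age and BMI as predictors. Apply the two-of-three rule in each imputed dataset and pool as in 6.1.1.1.
3. For that analysis only, replace the split rule in 6.1.2 and the set-to-missing rules for split and two-missing pairs in 6.1.1.1, 6.1.2 and 6.4.1. Leaving the two-missing rules in place would block the read-level imputation.
4. Keep explicit text that such pairs are excluded from observed cases and scored no improvement in the worst-case analysis. The last bullet of 6.4.1 now carries those rules for split pairs, so it must be rewritten rather than deleted. Pairs with two agreeing reads keep their result.

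In a simulation with 60 subjects per trial, latent correlation 0.4 and 5% of reads unusable, read-level imputation gave 70.0%, against 70.0% with all reads, 67.2% under 6.1.2 and 70.5% under 6.4.1.

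The cost is SAP wording and a modest change to the SAS code. The imputation model has three binary variables instead of one, with some added risk of separation. The site-merging rule in 6.4.5 already provides for non-convergence.

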6.4.2 Interim Analyses

In Stage 1, an initial cohort of 10 subjects will be enrolled. An interim database close and interim safety analysis of the first 10 subjects treated in Stage 1 will be conducted. This Stage 1 analysis will contain Week 2 safety data for the first 10 subjects treated. Safety analyses will be performed on the SP. Effectiveness data will not be included in the interim analysis.

Continuation to Stage 2 will be paused during evaluation of the Week 2 safety data from the first 10 subjects treated. All 10 subjects enrolled in Stage 1 will participate until Stage 1 study end, for a maximum duration of 90 days (\pm 7 days).

The interim analysis is only intended to obtain safety data for the first 10 subjects treated before starting recruitment for Stage 2. The interim analysis is not proposed to modify the study design, statistical analyses, or sample size, or for study termination, as this is not an adaptive study design. Since no effectiveness data are analyzed at interim, the interim analysis will not compromise the integrity of the study's effectiveness data, and it will not bias the final effectiveness analysis.

A separate statistical analysis plan for the interim analysis will be written.

6.4.3 Multiple Comparisons/Multiplicity

Primary analysis consists of two conditions which both need to be fulfilled to be able to claim effectiveness, therefore no adjustment of the type-1 error is needed.

6.4.4 Examination of Subgroups

The primary endpoint of observed cases will be additionally analysed by the different subgroups as described in section 6.1.1.3.

The safety endpoints for incidences of TEAEs using the SP will be descriptively summarized by Fitzpatrick skin type (I-III versus IV-VI) and race.

One subject might be present in multiple subgroups for race (White, Black or African American, Asian, American Indian or Alaska Native, Native Hawaiian or other Pacific Islander).

[figure not shown]
No statistical comparison of subgroups is planned.

6.4.5 Pooling of Sites

[figure not shown]
Analysis will be performed on pooled data across all sites.

Treatment site will be used as explanatory variable for the multiple imputation model. In case it turns out that convergence of the model cannot be accomplished, the two smallest sites will be merged and a new model will be calculated. This process will be repeated until convergence is established.

CCI

CCI

8 References

[1] Anne Lott & Jerome P. Reiter (2018): Wilson Confidence Intervals for Binomial Proportions With Multiple Imputation for Missing Data, *The American Statistician*, DOI: 10.1080/00031305.2018.1473796
